#### 924 11 Risks and Benefits to Participants

925 This is a phase III, double-masked, placebo-controlled randomized clinical trial (RCT)

evaluating the efficacy and safety of Elmiron® and hydroxyzine in participants with interstitial
cystitis (IC). After evaluation of previous study data and physician participant records using
these drugs in relation to IC, it is anticipated that there will be a direct benefit to the participants,
however, direct benefits are not guaranteed. The information gained from this study may
eventually prove beneficial to the treatment and diagnosis of other IC participants. Potential

risks to the participants are limited to risks related to venipuncture and the use of the study drugs.

#### 932 **12** Adverse Events and Participant Withdrawals

933 The Investigator (s) will be required to provide appropriate information concerning any findings
934 that suggest significant hazards, contraindications, adverse events, or precautions pertinent to the
935 safety of the drug under investigation.

- 936 12.1 Types of adverse events
- 937 An adverse event is any unfavorable and unintended sign, symptom, or disease
  938 temporarily associated with the use of a medicinal product, whether or not considered
  939 related to the medicinal product (57).
- 940 The term "adverse event" could include, but not be limited to, any of the following 941 events, which develop or increase in severity during the course of the study:
- Any signs or symptoms whether thought to be related or unrelated to the condition under study;
- Any clinically significant laboratory abnormality;
- Any abnormality detected during physical examination.

946These data will be recorded on the appropriate CRFs, regardless of whether they are947thought to be associated with the study or the drug under investigation. (Associated with948the use of the drug means that there is a reasonable possibility that the event may have949been caused by the drug.)

- Any event reported by the participant, other than mild sedation, that the participant considers an adverse event, will be immediately reported to the treating urologist.
- 952Signs and symptoms will be graded by the Research Coordinator as mild, moderate, or953severe.

Adverse events will be addressed at each participant visit and if noted by the participant,
a detailed description of the adverse event will be recorded on the Adverse Event CRF.
Adverse Event CRFs will be reviewed regularly by the DCC and reports will be produced

- 957 on a monthly basis summarizing the adverse events by clinical center and masked958 treatment assignment.
- 959 The following drug reactions may have been reported:
- 960 Elmiron®: Adverse events with Elmiron® tend to be infrequent, mild and transient.
- 961 Known adverse events include: diarrhea, nausea, alopecia (reversible upon
- discontinuation), headache, rash, dyspepsia, abdominal pain, liver function abnormalities,and dizziness. The above mentioned adverse events occurred at a frequency of 1% to 4%.
- 964 Hydroxyzine: Adverse experiences seen with hydroxyzine include temporary drowsiness
  965 and dry mouth. This drowsiness usually disappears after a few days in most people. This
  966 drug should not be taken together with alcohol, or other central nervous system
  967 depressing drugs, sedatives or sleep inducing medicines, including over-the-counter cold
  968 medicines that contain antihistamines, because there may be pronounced drowsiness. In
  969 dosages considerably higher than the study medication, participants may have urinary
  970 retention (inability to urinate), nightmares, weight gain or some shakiness in their hands.
- 971 Placebo: Inactive agent—No adverse events expected
- 972 12.2 Serious adverse events
- 973 A serious adverse event (SAE) is any adverse event occurring during the course of a 974 clinical investigation, whether or not determined to be related to exposure to the test 975 article, that is fatal or life-threatening, is persistent or significantly 976 disabling/incapacitating, requires in-patient hospitalization or prolongs hospitalization, or 977 is a congenital anomaly. Important medical events that may not result in death, be life-978 threatening, or require hospitalization may be considered an SAE when, based upon 979 appropriate medical judgement, they may jeopardize the patient or subject and may require medical or surgical intervention to prevent one of the outcomes listed in this 980 981 definition. (58)
  - 12.2.1 Reporting obligations

982

983

984

985

986

987

988

989

990

991

992

993

994

- Serious adverse events, whether or not unexpected or considered to be associated with the study, must be communicated to (see list below) immediately upon discovery of the event either by telephone, or fax.
- The RC will evaluate the potential SAE in consultation with the corresponding clinical site P.I. The NIDDK will notify the FDA. The reporting of serious adverse events in this study will involve recording any and all SAEs on the Serious Adverse Events form. Within 1 working day the following people or groups need to be notified via phone call. In addition, a fax of the SAE form, and mailed hard copy of the SAE will also be sent to these contacts:
- Clinical Site Principal Investigator
  - Respective Clinical Site IRB office
  - Data Coordinating Center
- 995The DCC will keep records of all SAE reports and report them to both the996NIDDK and the External Advisory Committee. The details of the reporting of

997the serious adverse events will be provided in the Study Manual of Procedures.998The Investigator must promptly inform the IRB or Ethics Committee of any999serious, unexpected adverse event that is considered possibly related to the1000study. Serious adverse experiences (deaths) need to be reported for a1001period of 30 days following cessation of study medication.

- 1002 12.3 Follow-up of adverse events
- 1003All serious adverse events must be followed with appropriate medical management until1004resolved.

#### 1005 12.4 Unmasking of treatment

1006 At the end of Baseline Visit 2, participants will be randomly assigned to one of the four treatment groups: 1) placebo and placebo, 2) placebo and Elmiron®, 3) hydroxyzine and 1007 placebo, or 4) Elmiron® and hydroxyzine, by a randomization schedule generated by the 1008 DCC. Neither the Investigator nor the investigational site personnel will know the 1009 treatment group to which any participant is randomized. If there is a serious adverse 1010 1011 event which is thought by the clinical site staff to be possibly or probably related to the 1012 coded medication, the clinical site staff, when necessary for the safety of the participant, 1013 will unmask treatment group assignment upon conferring with the clinical site's Principal 1014 Investigator. In this event, the clinical site staff must promptly contact the DCC with an 1015 explanation of the need for unmasking the treatment group assignment. A detailed report must also be submitted to the DCC within 3 working days of the initial DCC contact by 1016 1017 the Principal Investigator. Unmasking of treatment assignment is anticipated to be an uncommon occurance and is highly discouraged. 1018

# 1019 13 Administrative Aspects

## 1020 13.1 Institutional Review Board

1021 It is the responsibility of the Principal Investigator to provide the appropriate Institutional 1022 Review Board (IRB) with all pertinent material, including a copy of the informed 1023 consent. Approval of the protocol and the informed consent form must be obtained and 1024 forwarded to the sponsor prior to screening or enrolling any subjects. The Investigator 1025 also maintains the responsibility of initiating protocol reapproval, notification of protocol 1026 and/or consent form changes, notification of adverse reactions, and termination of the 1027 study according to the appropriate IRB requirements. A sample consent form is included 1028 in Appendix E.

1029 13.2 Laboratory accreditation

1030The Principal Investigator must maintain documentation of adequate licensure or1031accreditation for all clinical laboratory facilities used for study samples analysis. In1032addition, the clinical laboratory's normal values for test results must be forwarded to the1033DCC prior to study initiation. This documentation should cover the entire period the1034protocol is active.

#### 1035 13.3 Sponsor monitoring/on-site monitoring

1036The progress of the study will be carefully monitored by an experienced site-monitoring1037firm, for compliance with applicable government regulations and ICCTG protocol. These1038individuals will have access to all records necessary to ensure integrity of the data and the1039regulatory documents at the clinical sites.

#### 1040 13.4 Compliance with agencies

1041The sponsor will ensure this study is performed in compliance with applicable1042regulations associated with the Food and Drug Administration (FDA), the International1043Conference on Harmonization (ICH) (56)Guidelines and the Declaration of Helsinki.1044The sponsor will also keep a 1572 (Statement of Investigator), and current CVs of all1045Principal Investigators and Research Coordinators on file.

- 1046 13.5 Record retention
- 1047 The DCC must maintain all trial records for a period of 7 years.
- 1048 13.6 Direct access to source documents

1049 Investigators will maintain, on-site, in an orderly fashion, for a period of no less than 7
1050 years, and make available to the sponsor or the sponsor's representative, the following
1051 documents: the signed study protocol, amendments, informed consent documents,
1052 investigator brochure, approval letters from the IRB, drug accountability forms, CRFs, all
1053 primary source documentation, and all letters of correspondence.

- 1054 14 Data Management and Analysis
- 1055 The Data Coordinating Center (DCC) will coordinate all ICCTG activities pertaining to:
- Design, development, production, testing and distribution of case report forms (CRFs)
   over the internet to the client workstations at each clinical center;
- 1058 2. Collection, entry, verification, validation and query resolution of data; and
- 1059 3. Quality assurance monitoring and reporting.
- 1060 Data management issues, especially those concerning data quality and integrity in multicenter

trials, as discussed extensively in Meinert (59) DeMets (60) Neaton (61) Bailey (62), and

1062 McFadden (63), will be addressed within the Manual of Procedures (MOP) and emphasized

1063 during the Research Coordinator (RC) training prior to protocol initiation.

1064 The DCC will develop and maintain a computerized Data Management System (DMS) for this 1065 ICCTG Protocol, that will be deployed on client workstations within each of the main Clinical 1066 Centers and Satellite Centers. Case report forms (CRFs) will be available to be printed locally at 1067 the clinical centers from Portable Data Files (PDF). Originals of these forms will be retained by 1068 the clinical sites. Double data entry will be performed at the main Clinical Centers and Satellite 1069 Centers, utilizing the DMS tools available on the clients workstations. In particular, for the

1070 Baseline Visit 2, there will be a manual back-up system for implementing randomization of

- participants, in the event the DMS system is not functional at the moment that a newrandomization is required.
- 1073 Validation checks will be performed at the centralized database to verify data accuracy and
- 1074 identify missing, unclear, illogical, or problematic responses. Queries will be generated to
- 1075 resolve discrepancies. Confidentiality will be strictly adhered to by assigning a unique
- 1076 participant identifier that will not identify the subject by name. The Manual of Procedures will
- 1077 define these processes in detail.
- 1078 Details describing the transfer of urine specimens between the clinical sites and the Core
- 1079 Pathology Laboratory are presented in Appendix I.

# 1080 15 Statistical Considerations

1081 The proposed study design is a four-arm, double-blind, randomized clinical trial (RCT) utilizing 1082 a 2 × 2 factorial design to evaluate the effect of oral Elmiron® and/or oral hydroxyzine on IC 1083 symptoms. An inactive placebo will be used for both Elmiron® and hydroxyzine. The four 1084 treatment arms will be 1) placebo plus placebo, 2) placebo plus Elmiron® 3) hydroxyzine plus 1085 placebo 4) hydroxyzine plus Elmiron. A total of 136 participants will be enrolled. Details of the 1086 design considerations and statistical analysis, including sample size calculations, are described in 1087 the following sections.

1088 15.1 Randomization and Stratification

1089 The five treating Clinical Centers plus the two Satellite Centers compose the seven 1090 *Randomization Sites.* To ensure balance across treatment groups within each 1091 Randomization Site, a stratified randomization will be used. Within each of the seven 1092 strata, subjects will be randomly allocated in equal proportions to the four treatment arms 1093 using a permuted block randomization procedure with variable block sizes. In order to 1094 maintain blinding, each subject will be given a unique identifier number. The treatment 1095 code will be known only to the University of Pennsylvania Medical Center 1096 Investigational Drug Service and the Data Coordinating Center Quality Assurance 1097 Director until the completion of treatment and data collection on all participants.

1098 15.2 Sample Size Calculations

1099 This first ICCTG randomized clinical trial (RCT) represents a "pilot study" for which the 1100 primary goals are: (i) to demonstrate that the ICCTG network can accrue, follow and 1101 retain IC participants and collect relevant clinical trials data in an acceptable timeframe, (ii) to demonstrate safety and tolerability (including drop-out rates) for oral Elmiron® and 1102 oral hydroxyzine, and (iii) to conduct an initial efficacy evaluation of oral Elmiron® and 1103 oral hydroxyzine to determine whether any of the proposed treatments are worthy of 1104 further study in a larger comparative trial. As discussed subsequently, if there is evidence 1105 1106 of sufficiently high efficacy for any of the proposed treatments at the completion of this pilot study, accrual to some or all of the treatment arms may be expanded to provide 1107 1108 adequate statistical power for the comparison of response rates. Approximately 136 1109 participants, 34 per treatment arm, will be treated and followed for 24 weeks. The total

time required for this trial will be approximately 16 months, including the 24 weeks offollow-up on all participants.

1112 Although the primary objectives of this study are feasibility, safety and tolerability, the 1113 primary analysis on which sample size requirements are based is the comparison of response rates. Response will be defined based on the primary outcome of participant 1114 1115 assessment of improvement as measured at 24 weeks or withdrawal, whichever comes first. Participants who report being "moderately" or "markedly" improved at 24 weeks, 1116 as compared to their overall symptoms at the time of randomization, will be considered 1117 1118 "responders". Participants who withdraw from the study for any reason (e.g. adverse events or participant choice) will be considered treatment failures. All treatment failures 1119 1120 will be included in the denominator for evaluation of response rates.

For each of the two primary comparisons (Elmiron® versus no Elmiron®, hydroxyzine 1121 versus no hydroxyzine), we desire adequate numbers of participants to detect a difference 1122 in response rates between 30% and 65% (difference of 35%). The baseline response rate 1123 1124 of 30% is based on previous IC studies and other studies suggesting that this is a typical placebo rate for symptom-related outcomes. Assuming 80% power to detect the specified 1125 difference between groups at a two-sided  $\alpha = 0.05$  level of significance using the Fisher's 1126 1127 exact test, a minimum of 72 total participants are required for the two primary comparisons. After adjustments to allow for multiple comparisons in the factorial design 1128 1129 (50% increase), clustering within Randomization Site (20% increase), and interim 1130 monitoring (5% increase), a total of 136 participants or 136/4 = 34 participants per arm 1131 will be required. Total required sample sizes for alternative response rate differences are 1132 shown in the table below.

Smaller	Larger Response Rate									
Response Rate	30%	35%	40%	45%	50%	55%	60%	65%	70%	
10%	276	196	144	112	92	76	68	56	48	
20%	1168	572	344	236	168	132	104	84	72	
30%	-	5360	1424	664	392	260	184	136	108	
40%	-	-	-	5952	1540	704	408	264	184	
50%	-	-	-	-	-	6068	1540	688	392	

1135

1133 1134

In addition, for each individual treatment arm of 34 subjects, the width of a 95%
confidence interval for adverse event and other rates will be no wider than ± 17.5%. It is
expected that these 136 participants can be accrued within approximately 10 months.
Allowing for an additional 24 weeks of follow-up on all participants, the entire study
should require 16 months for completion.

#### 1141 15.3 Intent-toTreat Analyses and Missing Data

1142 An *intent-to-treat* analysis, in which all available data on all randomized participants are 1143 included, will be used for the primary comparison of treatments. All attempts will be 1144 made to keep missing data to a minimum and participants who withdraw from treatment will be encouraged to continue on study in order to provide complete follow-up 1145 information. However, it is expected that up to 30% of the randomized participants may 1146 1147 withdraw prior to the final assessment of response at 24 weeks. These participants will 1148 be included in the denominator for evaluation of the response rate primary endpoint. The 1149 characteristics at time of randomization for those participants without complete follow-up 1150 will be examined; however, there will be limited statistical power to detect any but major 1151 differences between these participants and those with complete follow-up. In addition, in order to assess the potential biases introduced by differential withdrawal among treatment 1152 1153 arms, a comparison of withdrawal rates and time to withdrawal will be included as an 1154 ancillary analysis to the primary endpoint comparison.

#### 1155 15.4 Statistical Analyses

1156In addition to the analyses described subsequently, descriptive statistics will be used1157during the course of the project as part of data management procedures for monitoring1158data quality. A brief overview of some of the statistical methods that may be used at the1159time of analysis, both for descriptive purposes and in more comprehensive analysis of the1160primary research questions, is summarized in the following sections. It is recognized that1161these methods may be revised and additional ones considered as the details of the specific1162analyses are developed.

1163 Descriptive Analyses: Standard descriptive statistics will be used to describe baseline 1164 characteristics and follow-up measures, both overall and within each treatment group. Examination of baseline characteristics will include estimates of the distribution of age, 1165 race, and other demographic characteristics, baseline severity based upon 1166 1167 pain/discomfort, urgency and frequency, and Randomization Site. These factors will be examined, both separately for each of the seven Randomization Sites, and combined 1168 1169 across centers. Summary statistics such as means, medians, and ranges will be produced 1170 for all measured variables. Frequencies will be computed for all categorical and ordinal 1171 variables. Graphical methods including stem-and-leaf diagrams and boxplots will be used to examine distributions, identify potential influential points, and guide in the choice 1172 of transformations if warranted. The balance of baseline measures across the treatment 1173 1174 groups will be compared using appropriate 2-sample and k-sample tests including analysis of variance (ANOVA), Wilcoxon and Kruskal-Wallis tests, and Fisher's exact 1175 1176 tests.

1177 Analysis of Primary Outcome: The primary analysis comparing response rates will make 1178 use of the exact conditional test (ECT) version of Mantel-Haenszel methods to adjust for within-center clustering, as implemented within the Proc-StatXact software system (64). 1179 Secondary analyses of the primary endpoint will rely on logistic regression and 1180 generalized estimating equation (GEE) methods to evaluate whether observed 1181 differences, if any, are attributable to imbalances in prognostic factors such as baseline 1182 1183 symptom severity (65). Standard regression diagnostics will be used to assess model 1184 adequacy and examine potential outlying or influential data points. In addition, time to

response will be compared among groups using standard methods for failure-time data,
including Kaplan-Meier curves, logrank tests, and Cox proportional hazards modeling
(66).

1188 Secondary Analyses: A number of secondary analyses will be conducted both to evaluate the secondary symptom-related outcomes and to supplement the primary endpoint 1189 1190 comparison. Secondary outcomes include pain and urgency measured on the Likert scales, urinary frequency and volume measures obtained from the voiding diary, the IC 1191 Symptom and Problem Index, the University of Wisconsin Symptom Survey, the Health 1192 Status Questionnaire (MOS SF-36), and the MOS Sexual Functioning Scale. Other 1193 1194 outcomes to be used in the final assessment include withdrawal rates and the use of 1195 narcotic medications for pain control.

- 1196 Profiles of symptom changes over time as collected from the symptom questionnaires and 1197 voiding logs will be compared among treatment groups using methods for longitudinal 1198 data analysis (67). These methods will include random effects regression models for 1199 continuous outcomes and GEE methods for categorical and ordinal outcomes (67). Both within- and between-participant variability in these outcomes will be carefully assessed 1200 1201 to provide pilot data for future clinical trials. For measures obtained only at baseline and one follow-up time point, change from baseline will be compared among groups using 1202 analysis of variance (ANOVA) and regression methods. When applicable, additional 1203 1204 analyses of the symptom outcomes will include evaluation of time to response defined by specific changes in symptoms (e.g. 50% drop in symptom score). Associations between 1205 longitudinal changes in secondary outcomes and the overall participant assessment of 1206 1207 improvement will be used to supplement the primary endpoint analysis and evaluate the validity of the symptom scales for assessing change. 1208
- 1209 Changes in the distribution of "worst" symptoms from baseline to 24 weeks; as recorded on the symptom ranking cards, will be evaluated using a marginal homogeneity test (64). 1210 Withdrawal rates will be compared among arms using standard methods for failure-time 1211 1212 data as described above (66). As the use of narcotic medications to control pain may provide information on the effectiveness of the treatments under study, a secondary 1213 analysis of the primary endpoint will evaluate narcotic usage. For this secondary 1214 1215 analysis, participants who initiate narcotics or increase narcotic usage 33% or more above baseline will also be considered "failures". The secondary analysis will include these 1216 1217 failures in the denominator for assessment of response rates and also compare narcotic 1218 usage among the treatment arms.
- 1219 15.5 Data Safety and Monitoring and Interim Analyses

1220 In addition to the final data analysis and standard monitoring for adverse events and data quality, one interim analysis will be conducted for the primary safety and efficacy data 1221 after approximately one half (n = 68) of the participants have been accrued and followed 1222 1223 for 24 weeks. Given the projected accrual rates, it is expected that this will occur approximately 10 months into the conduct of this study. The results of these analyses 1224 1225 will be presented to the External Advisory Committee. The goal of this analysis is to 1226 identify major differences among treatment arms that might lead to early study closure 1227 for ethical reasons. The endpoints to be considered at the interim time point include the primary response endpoint, toxicity and adverse events, and withdrawal rates. For the 1228

1229 primary endpoint, the Lan and DeMets (68) analog to an O'Brien-Fleming boundary (69) 1230 will be used to calculate the nominal significance level to which interim p-values are compared. Only an "upper" boundary, which allows for closure in the case of evidence 1231 1232 of a treatment difference, will be used at this interim analysis. Assuming this analysis is conducted using 24-week data on 68 participants, corresponding to an information time 1233 of 50%, the boundary significance level to which the observed p-value will be compared 1234 1235 is 0.0031. As described above, sample sizes have been adjusted to account for this 1236 interim monitoring.

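### The primary exact Mantel-Haenszel test names centre as its only adjustment and pools over the other randomised drug: valid, but slightly wasteful of power when that drug works

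*Protocol*

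**What the plan says.** - Section 15.4 (Analysis of Primary Outcome) specifies "the exact conditional test (ECT) version of Mantel-Haenszel methods", with the stated purpose of allowing for clustering by centre. No other stratifier is named for the primary test. The secondary logistic and GEE models mention baseline severity as an example, but not the other drug.
- Section 15.2 sets the comparisons: "For each of the two primary comparisons", Elmiron against no Elmiron and hydroxyzine against no hydroxyzine. With 34 participants per arm, each is 68 against 68, and half of each side takes the other drug.
- Section 15.1 allocates equally to the four arms within seven Randomization Sites, "using a permuted block randomization procedure with variable block sizes". The other drug is therefore a known design factor, close to balanced within each site.
- Section 15.4 opens by describing its methods as an overview that may be revised as details are developed.

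**The concern.** If hydroxyzine works, the Elmiron group and its control group are each a mixture of low and high responders, and the same holds with the drugs exchanged. A test that ignores the mixture uses too large a null variance, so it rejects less often than it could. The loss arises when one drug is active, which is the case a factorial design is meant to exploit. Power is also scarce at the effect section 15.6 would ideally like to detect (30% v 50%): about 60% with 136 participants.

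**Working it through.** **1. The plan's sample size reproduces.** Inputs from section 15.2: 30% v 65%, 80% power, two-sided 0.05, Fisher's exact test.

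- The normal-approximation formula gives 30.75 per group, or 36.2 with continuity correction. Exact enumeration of Fisher's test gives power 0.786 at 36 per group and 0.806 at 37. The stated 72 in total is consistent with this.
- 72 × 1.50 × 1.20 × 1.05 = 136.08, which gives 136.

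**2. Why the pooled test is conservative (large-sample check, site ignored).** Assume effects add on the log-odds scale. Let the tested drug move response 30% to 50% and the other drug 30% to 65%.

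- Odds ratios: (0.50/0.50)/(0.30/0.70) = 2.33 and (0.65/0.35)/(0.30/0.70) = 4.33. Both drugs together: odds 0.4286 × 2.333 × 4.333 = 4.333, a response rate of 0.8125.
- Margins for the tested drug: (0.50 + 0.8125)/2 = 0.656 v (0.30 + 0.65)/2 = 0.475, a difference of 0.181.
- Null variance, pooled: 0.5656 × 0.4344 = 0.2457. Stratified by the other drug: (0.40 × 0.60 + 0.7313 × 0.2687)/2 = 0.2183. Actual variance under balanced allocation: (0.21 + 0.25 + 0.2275 + 0.1523)/4 = 0.2100.
- Multiplying each by 2/68 and taking the root gives standard errors 0.0850, 0.0801 and 0.0786.
- Power, pooled: Φ((0.1813 − 1.96 × 0.0850)/0.0786) = 57.4%. Stratified: Φ((0.1813 − 1.96 × 0.0801)/0.0786) = 62.1%. The gain is 4.7 points.
- Size when the tested drug is inert and the other moves 30% to 65%: pooled variance 0.475 × 0.525 = 0.2494, actual (0.21 + 0.2275)/2 = 0.2188. The effective critical value is 1.96/√(0.2188/0.2494) = 2.09, so true size is about 3.6% instead of 5%.

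**3. Exact test, simulated.** 136 participants, seven near-equal sites, permuted blocks; 20,000 trials per power scenario. The exact conditional p-value was computed with 7 strata (site) and with 14 (site × other drug). Power in the table is at alpha 0.05 with p-values by probability ordering. The last column also covers doubled one-sided p-values and alpha 0.025, since section 15.2 allows for two comparisons without stating the level per test.

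| Tested drug | Other drug | 7 strata | 14 strata | Gain, all variants |
|---|---|---|---|---|
| 30→50% | inert | 62.4% | 62.6% | −0.3 to +0.2 |
| 30→50% | 30→50% | 61.7% | 63.0% | +1.3 to +3.2 |
| 30→65% | 30→65% | 94.6% | 96.1% | +1.3 to +2.3 |
| 30→50% | 30→65% | 53.1% | 58.9% | +5.1 to +6.2 |

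- Type I error at nominal 5%, other drug 30→65%: 3.1% (7 strata) v 4.3% (14 strata) by probability ordering; 2.5% v 3.4% with doubled p.
- For the last row of the table, unequal sites gave +4.8 to +6.5 and site variation (SD 0.5 on the logit) +4.6 to +5.4.
- If risk differences add (cells 30/50/65/85%), the gain is 6.2 to 7.2 points. If the combination adds nothing over the better drug (30/50/65/65%), it is 1.3 to 2.0 points.

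**4. Interim (section 15.5: n = 68, level 0.0031), assuming the same test is used.** Tested drug 30→65%.

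- Other drug inert: 42.4% v 41.0% by probability ordering, 39.3% v 37.7% with doubled p. The 14 strata cost about 1.5 points.
- Other drug 30→65%: 24.9% v 29.6%, and 21.6% v 25.6%. The 14 strata gain 4 to 5 points.

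**The case against.** The strongest reply is that the protocol never says site is the sole stratifier. That is read from centre being the only factor named, in a section that presents itself as a revisable overview, and a full list of strata could sit in an analysis plan not seen here. This stands as a limit. But the protocol did choose a stratified primary test and did state what it adjusts for, so the point concerns a stated choice.

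Second, the large gap is a corner case. It needs a 35-point effect of the other drug, which section 15.6 calls unlikely, together with a moderate effect of the tested drug. At the effect the trial was sized for, power is near 90% or above either way. With interaction, which section 3.3 contemplates, the gain also shrinks: 17.5% v 17.8% for cells 30/50/50/50%, and 50.3% v 52.2% for 30/30/30/65%. All of this stands and sets the size of the finding.

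Third, a reader might infer that the primary test is biased or that its odds ratio is wrong. Neither is supported. The test holds its level. In the case worked above the pooled odds ratio is (0.656/0.344)/(0.475/0.525) = 2.11, against 2.33 within strata. That is non-collapsibility: two different summaries, and section 15.4 speaks of response rates without naming an odds-ratio estimand.

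Fourth, one might fear that 14 small strata cost exact-test power. At the final analysis they do not materially. At the interim they cost a little if the other drug is inert.

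**Conclusion.** This is a small, avoidable inefficiency in the primary test, not a threat to validity. The expected loss is 1 to 3 points of power in the more plausible cases where the other drug works, and 5 to 6 points in the one unfavourable combination. There is none if the other drug is inert. It would be too strong to say that adding the factor has no downside: the interim cost of about 1 to 1.5 points with an inert other drug is real, though small beside the 4 to 5 points gained there if the other drug has the design effect.

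The figures rest on assumptions the protocol does not fix: site sizes, block sizes (4 and 8), the scale on which effects add, the two-sided p-value definition and the alpha per comparison. The direction was the same across the active-drug scenarios examined. The size depends mainly on how strong the other drug is.

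**What to change.** In section 15.4, define the primary test for each drug as the exact conditional Mantel-Haenszel test stratified by the seven Randomization Sites and by assignment to the other drug (14 strata), and report the common odds ratio from the same strata. Say that the interim test in section 15.5 uses the same strata. If an analysis plan already names the second stratifier, bring 15.4 into line with it.

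The cost is a phrase: the same software procedure, no added participants, and type I error still below 5%. Settle it before any unblinded look, because a stratifier added afterwards under the section's general freedom to revise methods would be open to challenge.
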